#### **Serious Adverse Reaction (SAR)**

A serious adverse reaction is an SAE that is suspected as having a causal relationship to the trial treatment (SBRT), as assessed by the investigator responsible for the care of the patient. A suspected causal relationship is defined as possibly, probably or definitely related (see definitions of causality table).

**Definitions of causality**

| Relationship   | Description   |
|----------------|---|
| Unrelated      | There is no evidence of any causal relationship with the trial treatment  |
| Unlikely       | There is little evidence to suggest there is a causal relationship (e.g. the event did not occur within a reasonable time after administration of the trial treatment). There is another reasonable explanation for the event (e.g. the patient's clinical condition, other concomitant treatment)            |
| Possible       | There is some evidence to suggest a causal relationship (e.g. because the event occurs within a reasonable time after administration of the trial treatment). However, the influence of other factors may have contributed to the event (e.g. the patient's clinical condition, other concomitant treatments) |
| Probable       | There is evidence to suggest a causal relationship, and the influence of other factors is unlikely  |
| Definitely     | There is clear evidence to suggest a causal relationship, and other possible contributing factors can be ruled out  |
| Not assessable | There is insufficient or incomplete evidence to make a clinical judgement of the causal relationship.   |

**Related Unexpected Serious Adverse Event**

An adverse event that meets the definition of serious and is assessed by the CI or nominative representative as:

- “Related” – that is, it resulted from administration of any of the research procedures, and
- “Unexpected” – that is, the type of event is not listed in the protocol as an expected occurrence (see appendix 3)

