### **11.4. Review of Serious Adverse Events**

The Chief Investigator (or designated representative) will assess all reported SAEs for causality and expectedness (NB. The Chief Investigator cannot down-grade the Principal Investigator's assessment of causality.)

SAEs assessed as having a causal relationship to study treatment and as being unexpected will undergo expedited reporting to the relevant authorities and all other interested parties by ICR-CTSU (see 11.5).

Sites should respond as soon as possible to requests from the Chief Investigator or designated representative (via ICR-CTSU) for further information that may be required for final assessment of an SAE.

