### **11.5. Expedited Reporting of Related Unexpected SAEs**

If an SAE is identified as being related and unexpected by the Chief Investigator it will be reported by ICR-CTSU to the main REC, the Sponsor and all other interested parties within 15 days of being notified of the event.

The Principal Investigators at all actively recruiting sites will be informed of any related unexpected SAEs occurring within the trial at appropriate intervals.

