#### **Bowel changes**

**Grade 0:** No symptoms

**Grade 1:** Increased frequency or change in quality of bowel habits not requiring medication/rectal discomfort not requiring analgesics.

**Grade 2:** Diarrhoea requiring parasympatholytic drugs/mucous discharge not necessitating sanitary pads/rectal abdominal pain requiring analgesics.

**Grade 3:** Diarrhoea requiring parenteral support/severe mucous or blood discharge necessitating sanitary pads/abdominal distention (flat plate radiograph demonstrates distended bowel loops).

**Grade 4:** Acute or subacute obstruction, fistula or perforation/GI bleeding requiring transfusion/abdominal pain or tenesmus requiring tube decompression or bowel diversion.

**Grade 5:** Death directly due to radiation morbidity.

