### A3. Expected serious adverse events

The following are possible anticipated treatment related AEs (i.e. expected occurrences), ≤CTCAE Grade 3, which are not subject to expedited reporting to ICR-CTSU but all such events should be reported in the appropriate section of the CRF.

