#### SBRT

- Urinary toxicities:
  - Urinary frequency/urgency/nocturia
  - Urinary retention
  - Urinary obstruction/strictures
  - Haematuria
  - Cystitis/bladder spasms
  - Urinary incontinence/leakage
  - Pain (prostate, urinary/dysuria)
- GI Toxicities:
  - Pain (rectal, pelvic, abdominal)
  - Diarrhoea
  - Constipation
  - Rectal bleeding/ulcer
  - Fistula
  - Proctitis
  - Bowel obstruction or perforation
- Sexual function
  - Erectile dysfunction
  - Decreased volume of ejaculate/absence of ejaculate
  - Decreased libido
- Dermatology/Skin
  - Rash
  - Hair loss in treatment area
- Bone fractures
- Lymphodema
- Related to fiducial marker insertion
  - Bleeding
  - Sepsis (urinary and systemic)
  - Pain

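### Section 11.1 tests expectedness by type of event, A3 caps its expected list at CTCAE grade 3, and the text does not settle how a related grade 4-5 event of a listed type is classed

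*Protocol*

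**What the plan says.** Section 11.1 of the protocol defines a related unexpected SAE by two limbs. The event must have resulted from a research procedure, and it must be unexpected, meaning that "the type of event is not listed in the protocol as an expected occurrence (see appendix 3"). No grade or severity criterion appears in that definition.

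Appendix A3 opens its list with a grade limit: "The following are possible anticipated treatment related AEs (i.e. expected occurrences), ≤CTCAE Grade 3". The entries below are bare event types without grades of their own. Under SBRT they include "Bowel obstruction or perforation" and fistula, and sepsis appears among the events related to fiducial marker insertion.

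The classification is used in sections 11.4 and 11.5. The Chief Investigator or a representative "will assess all reported SAEs for causality and expectedness". Then "SAEs assessed as having a causal relationship to study treatment and as being unexpected will undergo expedited reporting to the relevant authorities". Section 11.5 sets the deadline for reporting to the main REC, the Sponsor and other interested parties at "within 15 days of being notified of the event". It also uses the related and unexpected category to decide which events are notified to investigators at recruiting sites.

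**The concern.** A definition that asks only whether a type is listed gives the same answer at every grade. A list that stops at grade 3 does not. The two therefore part at grades 4 and 5, that is, for life-threatening and fatal events. Once an event is judged related, expectedness is the only remaining gate to the 15-day report and the site alerts.

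Two competent assessors could classify the same treatment-related death differently, and each could cite the protocol. The protocol itself singles out GI toxicity for attention in section 12.3.2 because PPN-SBRT raises the bowel dose. Severe bowel events are therefore a foreseeable use of this rule.

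**Working it through.** No arithmetic applies, so the check sets the texts side by side.

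**Inputs.** The expectedness test (11.1), the list and its grade limit (A3), the gate and its consequences (11.4 and 11.5), and the SAE window, which closes 30 days after last treatment (11.1 and 11.3).

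**Step 1: apply each text to a related, serious bowel perforation within the window.**

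| Grade | 11.1, read literally | A3, with its limit | Agree? |
|---|---|---|---|
| 3 or lower | Type is listed: expected, no 15-day report | Within limit: expected, no 15-day report | Yes |
| 4 or 5 | Type is listed: expected, no 15-day report | Above limit: not an expected occurrence, 15-day report | No |

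The same split holds for any listed SBRT or fiducial type that reaches grade 4 or 5.

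**Step 2: look for a sentence that settles it.** Section 11.4 assigns the expectedness judgement and section 11.5 attaches the deadline, but neither says how it is made. A3 does not say that its limit governs that judgement. Its introduction speaks of "possible anticipated treatment related AEs (i.e. expected occurrences), ≤CTCAE Grade 3, which are not subject to expedited reporting to ICR-CTSU". That phrase concerns reporting from site to trials unit, whereas 11.4 and 11.5 concern the later step from the unit to the REC and Sponsor. No other section says how a listed type above grade 3 is to be classed.

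**Step 3: see what remains on the literal reading.**
- Section 11.3 requires all SAEs to reach ICR-CTSU within 24 hours. A3's exemption cannot remove a grade 4-5 event from that duty, because the exemption stops at grade 3.
- The annual report (11.7) covers related unexpected SAEs and also any safety concerns that arose.
- The IDMC reviews safety at least annually, and reviews acute toxicity once 82 PPN-SBRT patients have 12 weeks of follow-up (12.5). Its summaries can go to the main REC if required (13.3).

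What is exposed is therefore the 15-day report and the site alerts under 11.5.

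**The case against.** The strongest reply is that there is one rule, not two. Section 11.1 sends the reader to appendix 3 and uses the same term, expected occurrence, that A3 defines with its grade limit. On that view a grade 4-5 perforation is simply not listed as an expected occurrence. This is a sensible reading and may be what was intended. It means that a reader who infers a flat contradiction, or who takes 11.1 to declare severity irrelevant, goes further than the text. But 11.1 names type as the test, a perforation is a listed type at any grade, and A3 attaches its limit to a different reporting step. The reading is available but not secured.

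Four further inferences are tempting, and the documents do not support them:

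- *That these events would vanish from oversight or from the annual report.* The 24-hour report, the IDMC reviews and the safety-concerns part of the annual report all remain.
- *That myocardial infarction and stroke on the ADT list are caught.* ADT is standard care here. An event attributed to it would not normally meet the related limb, so expectedness would not decide its reporting.
- *That every grade 4-5 event of a listed type is affected.* SAEs count only up to 30 days after last treatment. A later fistula or perforation lies outside SAE reporting under either text.
- *That perforation is always above the limit*, because the RTOG acute bowel scale in A2 places "Acute or subacute obstruction, fistula or perforation/GI bleeding requiring transfusion" at grade 4. A3 counts CTCAE grades, so the RTOG grade shows only that the protocol regards such events as severe.

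**Conclusion.** The point holds as an unresolved ambiguity in a safety definition. For related SAEs of a listed SBRT or fiducial type, at CTCAE grade 4 or 5 and within 30 days of last treatment, the literal wording of 11.1 and the limit in A3 lead to opposite decisions on the 15-day report and the site alerts. At grade 3 or lower they agree.

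The conclusion assumes that type in 11.1 is read in its ordinary sense, without grade. For the fiducial entries it also assumes that marker insertion counts as a research procedure. The number of events affected cannot be derived from the protocol. No endpoint, analysis or sample size depends on this. It should still be corrected, because the events concerned are the gravest and the repair is small.

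**What to change.** Reconcile 11.1 and A3 so that one expectedness rule applies, using the limit the protocol already has. In 11.1, define unexpected along these lines: *the type or severity of the event is not listed in appendix 3 as an expected occurrence; a listed event type above CTCAE grade 3 is unexpected.* In A3, add a sentence saying that its grade limit governs the expectedness assessment in 11.4 and 11.5.

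The cost is about one sentence in each place and, in practice, a few additional 15-day reports.

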**11.2. Reporting Adverse Events to ICR-CTSU**

Any toxicity, sign or symptom that occurs after commencement of first study intervention, which is not unequivocally due to progression of disease, should be considered an AE.

All AEs must be reported on the relevant CRF and submitted to ICR-CTSU.

The severity of AEs should be graded according to the NCIC-CTC criteria v 5.0. For each AE, the highest grade observed since the last visit should be reported.

Whenever one or more toxicity/sign/symptom corresponds to a disease or a well-defined syndrome only the main disease/syndrome should be reported.

### **11.3. Reporting of Serious Adverse Events to ICR-CTSU**

Any SAE that occurs after the first study intervention and up to 30 days following the last administration of study treatment must be reported.

All SAEs should be reported to ICR-CTSU within 24 hours of the Principal Investigator (or designated representative) becoming aware of the event, by completing the PACE-NODES SAE form and faxing to:

The ICR-CTSU safety desk

Email: [[contact]](mailto:[contact])

For the attention of the PACE-NODES Trial team

As much information as possible, including the Principal Investigator's assessment of causality, must be reported to ICR-CTSU in the first instance. Additional follow up information should be reported as soon as it is available.

All SAE forms must be completed, signed and dated by the Principal Investigator or designated representative.

### **11.4. Review of Serious Adverse Events**

The Chief Investigator (or designated representative) will assess all reported SAEs for causality and expectedness (NB. The Chief Investigator cannot down-grade the Principal Investigator's assessment of causality.)

SAEs assessed as having a causal relationship to study treatment and as being unexpected will undergo expedited reporting to the relevant authorities and all other interested parties by ICR-CTSU (see 11.5).

Sites should respond as soon as possible to requests from the Chief Investigator or designated representative (via ICR-CTSU) for further information that may be required for final assessment of an SAE.

### **11.5. Expedited Reporting of Related Unexpected SAEs**

If an SAE is identified as being related and unexpected by the Chief Investigator it will be reported by ICR-CTSU to the main REC, the Sponsor and all other interested parties within 15 days of being notified of the event.

The Principal Investigators at all actively recruiting sites will be informed of any related unexpected SAEs occurring within the trial at appropriate intervals.

**11.6. Follow up of Serious Adverse Events**

SAEs should be followed up until clinical recovery is complete or until disease has stabilised. SAE outcomes should be reported to ICR-CTSU using the relevant section of the SAE form as soon as the Principal Investigator or designee becomes aware of the outcome.

[figure not shown]
**11.7. Annual Safety Reporting**

An annual progress report will be provided to the main REC by ICR-CTSU and copied to the Sponsor at the end of the reporting year. This will include data about related unexpected SAEs and whether any safety concerns have arisen during the reporting period.

**11.8. Reporting Pregnancies**

If any trial participants' partner becomes pregnant while receiving trial treatment or up to 12 months after receiving trial treatment, this should be reported to ICR-CTSU using the pregnancy reporting form. Participants who become pregnant should discontinue from trial treatment immediately. Pregnancies should be followed up until conclusion and all follow-up information should be reported to ICR-CTSU. If the outcome of the pregnancy meets the definition of serious (i.e. congenital abnormality) this should be reported to ICR-CTSU following the serious adverse event reporting procedures described above.

Figure 2: Flow diagram for SAE reporting, and action following report

NB. All SAEs should continue to be followed up as specified above

## 12. STATISTICAL CONSIDERATIONS

### 12.1. *Statistical Design and Sample Size Justification*

This is a multicentre, phase III, randomised trial with the primary aim of determining superiority of PPN-SBRT over P-SBRT in terms of time to biochemical or clinical failure.

#### 12.1.1. *Sample size for primary efficacy analysis*

The sample size calculation is based on assessing time to biochemical or clinical failure (primary endpoint), as defined below. In POP-RT, 5-year biochemical failure-free survival in the control arm was 81% [10]. Allowing for some improvement in outcomes over time, as suggested by recent data from PACE-B which showed very good outcomes in the lower-risk group [18] the 5-year event-free rate in the P-SBRT control arm is assumed to be 85%. The target hazard ratio (HR) for the trial is 0.6, corresponding to a 6% improvement (to 91%) in the 5-year event rate with PPN-SBRT. Although a larger effect (HR=0.23) was seen in POP-RT, the PACE-NODES design will ensure that a smaller but clinically meaningful effect is not missed. The target effect size is similar to that for PIVOTALboost (HR=0.625), which is testing the same question in the 20f setting in a lower risk group of patients, reflecting the magnitude of effect considered appropriate to counterbalance a likely increase in toxicity.

The sample size was calculated using the `artsurv` package (v1.1.0) within Stata software and was based on the following design parameters and assumptions:

- 1:1 allocation ratio
- staggered recruitment over 37 months in proportions of 5%, 13%, 16%, 21%, 21%, 21%, 3% per 6-month period (noting that recruitment is expected to be complete within the first month of the final period)
- 41 months minimum follow-up
- 80% power
- 5% 2-sided significance
- Expected 3% loss to follow-up at 5 years (based on CHHiP)

In order to achieve 80% power, 78 control arm events are required for the analysis (126 events expected in total), and we anticipate that this will be achieved through recruitment of 1128 patients, followed up for a minimum of approximately 3.5 years.

#### 12.1.2. *Changes to the sample size for primary efficacy analysis*

The sample size was increased (from an original target of 536) in version 3.0 of the protocol. The reasons for this change were:

- (i) to increase the expected event-free rate in the control arm (from 81% to 85% at 5 years) based on data from the PACE-B trial which suggested an improvement in outcomes over time; [18]
- (ii) to target a slightly more conservative effect size (changing the HR from 0.5 to 0.6) to ensure that a smaller, but clinically meaningful difference could be detected. This was

particularly because use of PSMA-PET for staging within PACE-NODES may be lower than in POP-RT, since other imaging options are permissible, and this has the potential to slightly dilute any observed benefit of PPN-SBRT when compared with the earlier trial.

In recalculating the sample size, the timelines and expected rates of accrual were also adjusted based on recruitment to the trial up to that point.

### **12.1.3. Power for secondary toxicity analysis**

This number of patients also gives adequate power for secondary toxicity comparisons, aimed at demonstrating “non-inferiority” of PPN-SBRT in terms of late gastrointestinal toxicity (CTCAE grade 2+), as follows:

Assuming a 92% evaluable rate (based on expected recurrence-free rate at 2 years and allowing for some loss to follow-up), 1038 patients would be evaluable for toxicity comparison up to 2 years. Assuming a P-SBRT toxicity rate of 13% (based on data from PACE-B [19]), the trial will have more than 85% power, with a one-sided 5% significance level, to rule out a PPN-SBRT toxicity rate of >19%, i.e. accepting an increase of up to 6% worse.

If toxicity rates are lower we will still have very good power (at least 90%) to rule out a doubling in toxicity. This relative non-inferiority margin (“a doubling”) is informed by POP-RT where the cumulative late RTOG grade 2+ gastrointestinal toxicity was 6.5% for WPRT and 3.8% for PORT [20]. Unless absolute rates are very low, we will have good power (>80%) to rule out smaller relative effects (E.g. with a 10% P-SBRT toxicity rate, we would have >80% power to rule out a 50% increase, to 15%, with PPN-SBRT).

## **12.2. Treatment Allocation**

All trial participants will receive Stereotactic Body Radiotherapy (SBRT).

Participants will be randomised between 5 fraction prostate SBRT (P-SBRT) or 5 fraction prostate and pelvic nodal SBRT (PPN-SBRT) on a 1:1 basis using minimisation with a random element. Balancing factors in the minimisation algorithm will be: centre, radiological staging method (PET-CT and/or whole body MRI; other), use of peri-rectal spacers (yes; no), use of chemotherapy/ARTA (yes; no), and planned duration of ADT (<2 years; ≥2 years).

## **12.3. Endpoint Definitions**

### **12.3.1. Primary endpoint**

Time to biochemical or clinical failure: defined as time from randomisation to first of biochemical failure, recommencement of androgen deprivation therapy, local recurrence, lymph node/pelvic recurrence, distant metastases or death due to prostate cancer. Recurrence identified on PSMA PET or wbMRI are included as events. For participants who are not known to have had an event at the time of analysis (including those lost to follow-up), observations will be censored on the date of most recent follow-up visit.

Biochemical failure is the most sensitive indicator of recurrent prostate cancer, encompassing clinical and radiological relapse, and is aligned with the primary outcome in PACE-C and PIVOTALboost.

Biochemical (PSA) failure will be defined following the RTOG-ASTRO Phoenix Consensus definition: an increase in serum PSA  $\geq 2$  ng/ml greater than the post-treatment nadir. PSA failure will be confirmed with a second measurement ( $>4$  weeks from the index measurement) also meeting the criteria for PSA failure.

### **12.3.2. Secondary endpoints**

A key secondary endpoint is late gastrointestinal (GI) toxicity, grade  $\geq 2$  (CTCAE, clinician assessed).

Assessment of GI toxicity is particularly important with PPN-SBRT given the increased bowel dose compared to prostate alone radiotherapy. CTCAE is a recognised standard used in other relevant trials. Given the potential for discrepancies between clinician and patient reported toxicity [21], patient reported outcomes measures (PROMs) as a measure of the direct impact on patient quality of life [22] will provide complementary information to clinician assessed toxicity.

Other secondary endpoints include:

- Time from randomisation to first of: recommencement of androgen deprivation therapy; biochemical failure; loco-regional recurrence (recurrence in the prostate and/or pelvic lymph nodes).
- Metastatic relapse-free survival, defined as time from randomisation to distant metastases or death from prostate cancer.
- Prostate cancer-specific survival, defined as time from randomisation to death due to prostate cancer.
- Overall survival, defined as time from randomisation to death from any cause.
- Acute toxicity, occurring within the first 12 weeks of follow-up (CTCAE and RTOG), with a focus on GI and GU toxicity, grade  $\geq 2$ .
- Late toxicity, reported from the 6 month visit onwards (CTCAE and RTOG), with a focus on GI and GU toxicity, grade  $\geq 2$ .
- Quality of life measured using the following questionnaires: the International Prostate Symptom Score (IPSS), the 5-item version of the International Index of Erectile Function (IIEF-5), the short form Expanded Prostate Index Composite-26 (EPIC-26) and the EQ-5D-5L (see section 19.2 for further details).

- Radiotherapy planning and delivery data (PTV for prostate and pelvic nodes; adherence to dose constraints; and deviations from allocated treatment arm) to demonstrate feasibility.
- Second primary cancers occurring during trial follow-up.

